## 4. CASE DEFINITION

It should be noted that for the reporting of safety (unsolicited AEs, AEs of special interest and SAEs), the investigator will use all available information and his/her medical judgment to make diagnoses. The case definitions presented below will be used for a safety analysis complementary to standard safety tabulations of events according to Medical Dictionary for Regulatory Activities (MedDRA) preferred terms.

### 4.1. RTI case definitions

During the analysis of the study, all cases identified during the surveillance of RSV-RTI will be definitively classified as either RTI, LRTI, severe LRTI or very severe LRTI according to the standardized case definitions (see [Table 6](#)) based on the available World Health Organization (WHO) case definitions [[Modjarrad](#), 2016].

**Table 6 Case definitions for data analysis**

Case	At sea level up to 2500 meters elevation	Above 2500 meters elevation
RSV-RTI	Runny nose OR blocked nose OR cough AND Confirmed RSV infection 	Same
RSV-LRTI	History of cough OR difficulty breathing  AND SpO 2 < 95%  , OR RR increase  AND Confirmed RSV infection 	Same but with SpO2 < 92%
severe RSV-LRTI	Meeting the case definition of RSV-LRTI AND SpO 2 < 93%  , OR lower chest wall in-drawing	Same but with SpO2 < 90%
very severe RSV-LRTI	Meeting the case definition of RSV-LRTI AND SpO 2 < 90%  , OR inability to feed, OR failure to respond / unconscious	Same but with SpO2 < 88%
RSV hospitalization	Confirmed RSV infection  AND Hospitalized for acute medical condition 	Same
All-cause LRTI	History of cough OR difficulty breathing  AND SpO 2 < 95%  , OR RR increase 	Same but with SpO2 < 92%

LRTI = lower respiratory tract infections; RR = respiratory rate; RTI = respiratory tract infections; SpO2 = blood oxygen saturation.

Based on [[Modjarrad](#), 2016]

 Based on history reported by parents.

 The lowest value during the course of illness will be used.

 RR increase defined as:

≥ 50/min (2 to 11 months of age)

≥ 40/min (12 months of age or above)

The highest value during the course of the illness will be used.

 RSV infection confirmed on nasal swab positive for RSV A or B by quantitative Reverse Transcription Polymerase Chain Reaction (qRT-PCR).

 RSV sampling and testing is based on medical judgment of medical practitioner or driven by algorithm.

 Hospitalization is defined as a medical decision that the infant requires admission for observation or treatment.

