##### Age at the time of FI-RSV vaccination

The four studies included children aged between 2 months and 9 years. When comparing the different age strata at which children were vaccinated in these studies (Young infants [0-5 months]; Older infants [6-11 months]; Toddlers [12-23 months]; Children [ $\geq$ 24 months]), the most prominent increase in RSV-associated LRTI and hospitalization following FI-RSV vaccination was observed in children vaccinated at younger age. In the study where the youngest subjects were vaccinated [[Kim, 1969](#)], 2 of the vaccinated children died, one at the age of 14 months, the other at the age of 16 months. Each had received three vaccine doses, the first one beginning at the age of 2 months, the other one at the age of 5 months.

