## 11.4. Determination of sample size

The sample size determination is based on the minimum number of subjects needed to allow detection of a serious ERD signal having a magnitude similar to that of the historic FI-RSV vaccine trials [Kim, 1969]. A total of 150 infants will be enrolled and randomized with 1:1:1 ratio to receive either 1 dose of the  $1.5 \times 10^{10}$  vp/dose ChAd-155 RSV vaccine [the 1D RSV + comparator group], 2 doses of the  $5 \times 10^{10}$  vp/dose ChAd-155 RSV vaccine [the 2D RSV + comparator group], or no ChAd-155 RSV vaccine [the comparator/Placebo control alone group].

[figure not shown]
An effect of vaccination on ERD will be monitored very closely. It is anticipated that at least 50% of subjects [Dunn, 2013] will have a negative RSV exposure status (at screening which will be assessed by in-stream serological testing of baseline samples). While the rate of RSV infection could be highly variable by season, a conservative rate of infection of 20% in the first season is assumed [Kutsaya, 2016]. Therefore, with 50 infants in each RSV vaccine group, it is anticipated to observe at least 5 infected infants with a negative RSV exposure status (at screening based on in-stream baseline serological testing) in each RSV vaccine group [ $50 \times 0.5 \times 0.2 = 5$ ].

With a one-sided type I error of 0.05, and the assumption of a 10% rate of infection progressing to very severe RSV-LRTI (which is a conservative assumption based on the rate in the natural history of disease), 5 infections can provide at least 90% statistical power to demonstrate the progression rate from infection to very severe RSV-LRTI is less than 80%. That is less extreme than that observed in the historic FI-RSV vaccine trial where 80% of RSV RTI cases progressed to hospitalization [Kim, 1969]. During the course of the study, since the actual negative RSV exposure status (at screening based on in-stream baseline serological testing) and infection rates may be lower than 50% and 20%, respectively, the sample size **may** be adjusted as needed through additional recruitment in order to achieve **a sufficient number of** RSV infected infants with a negative RSV exposure status (at screening based on in-stream baseline serological testing) in each RSV vaccine group (**Amended 1 August 2019**).

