## 11.11. Interpretation of analyses

For the occurrence of very severe RSV-LRTI among RSV infected infants with a negative RSV exposure status (at screening based on in-stream baseline serological testing) from first vaccination (Day 1) up to the end of the first RSV transmission season, if the upper boundary of the 95% one-sided lower CI of the rate is under 80%, it indicates that the very severe RSV-LRTI rate is less than that of the historic RSV-FI trials [[Kim, 1969](#)].

Comparative analyses will be exploratory and should be interpreted with caution considering that there is no adjustment for multiplicity and that group sizes are small for these comparisons.

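### Table 6 gives death no place, so a confirmed RSV infection that ends in death with no qualifying SpO2 or respiratory rate on file is scored as not having progressed

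*Protocol*

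**What the plan says.** Sections 4.1 and 11.6.4 of the protocol make Table 6 the final classification of every case found in surveillance. Table 6 (repeated as Synopsis Table 5) builds the severity grades in steps.

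- RSV-LRTI needs cough or difficulty breathing, then SpO2 below 95% or a raised respiratory rate, then confirmed RSV. Footnote 4 fixes the confirmation: "RSV infection confirmed on nasal swab positive for RSV A or B by quantitative Reverse Transcription Polymerase Chain Reaction (qRT-PCR".
- Very severe RSV-LRTI needs the RSV-LRTI definition to be met, and in addition SpO2 below 90%, "OR inability to feed, OR failure to respond / unconscious". The SpO2 limits are lower above 2500 m.
- For SpO2, "The lowest value during the course of illness will be used"; for respiratory rate, the highest.

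No row of the table mentions death.

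The statistical rule on enhanced RSV disease (ERD) uses the very severe category alone. Section 11.11 begins "For the occurrence of very severe RSV-LRTI among RSV infected infants with a negative RSV exposure status" and compares the upper confidence bound with 80%. Section 11.4 sets the design: "With a one-sided type I error of 0.05", "the assumption of a 10% rate of infection progressing to very severe RSV-LRTI", and the claim that "5 infections can provide at least 90% statistical power". It then gives two readings of the result: at most 1 progression in 5 excludes the historic rate, and at least 3 in 5 signals more than the 10% of natural infection.

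**The concern.** Death is the worst end of the severity scale that the rule is meant to measure, yet it is not a criterion. A death is scored as a progression only if the listed signs were recorded beforehand. If they were not, and the swab is positive, the infant stays in the denominator as infected and is missing from the numerator. The error then runs in the unsafe direction: a fatal RSV infection lowers the estimated progression rate and supports the statement that the FI-RSV level of risk has been excluded.

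That statement matters because the study is meant to support moving to infants from 6 weeks of age (Section 1.2.2.1). It also rests on very few infections, so a single misplaced case can settle it.

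**Working it through.** **How the case is scored.** Take an infant in the seronegative analysis set with a positive nasal-swab qRT-PCR who dies.

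1. RSV infection: yes, by footnote 4. The infant is in the denominator.
2. RSV-LRTI: requires a qualifying SpO2 or respiratory rate at some point in the illness. This fails if both are missing. It also fails if both were normal at an assessment visit (held within 72 hours for cough or runny nose, Sections 9.2.1 and 9.2.3) and the infant then died unobserved. A repeat visit is at the investigator's judgment (Section 9.2.4).
3. Very severe RSV-LRTI: requires step 2, so it fails. The infant counts as infected, not progressed.

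The AND/OR string in Table 6 has no brackets. Even if inability to feed or unresponsiveness could stand alone, death is still not listed.

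**The plan's own figures first.** Inputs from 11.4: n = 50 × 0.5 × 0.2 = 5 infections per vaccine group, true rate 10%, rate to exclude 80%, one-sided 0.05, rule at most 1 of 5. Exact binomial:

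- Power at 10%: 0.9^5 + 5 × 0.1 × 0.9^4 = 0.5905 + 0.3281 = 0.9185. The stated figure of at least 90% reproduces.
- Error at 80%, rule at most 1: 0.2^5 + 5 × 0.8 × 0.2^4 = 0.0003 + 0.0064 = 0.0067.
- Error at 80%, rule at most 2: 0.0067 + 10 × 0.8^2 × 0.2^3 = 0.0067 + 0.0512 = 0.0579, above 0.05. So 1 of 5 is the right cut-off.
- Alarm rule, at least 3 of 5 when the true rate is 10%: 0.0086. At least 2 of 5 would give 0.0815.

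**Effect of one unscored death.** The protocol names no interval method, so exact (Clopper-Pearson) one-sided 95% upper limits are assumed here:

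| Progressions / infections | Upper limit | 80% excluded? |
|---|---|---|
| 0/5 | 45.1% | yes |
| 1/5 | 65.7% | yes |
| 2/5 | 81.1% | no |
| 3/5 | 92.4% | no |
| 1/4 | 75.1% | yes |

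- One scored progression plus one unscored RSV death: 1/5 as written (80% excluded), 2/5 with the death counted (not excluded).
- Two scored plus one unscored: 2/5 as written, 3/5 with the death counted, which meets the alarm rule.
- If the death has no positive nasal swab, it leaves the denominator as well. One scored progression then reads 1/4, which also excludes 80%.

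The first result does not depend on the interval method: 2 of 5 already fails the count rule in 11.4.

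**Effect on the error rate.** The share of true progressions lost this way is not in the documents. Taking it as an assumption f, with a true rate of 80%, the scored rate is p = 0.8 × (1 − f) and the chance of wrongly excluding 80% is (1 − p)^5 + 5p(1 − p)^4:

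| f (assumed) | p | Chance of wrong exclusion |
|---|---|---|
| 0 | 0.80 | 0.7% |
| 6.25% | 0.75 | 1.6% |
| 12.5% | 0.70 | 3.1% |
| 25% | 0.60 | 8.7% |

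**The case against.** The strongest reply is that the path hardly exists. Either sign is enough for RSV-LRTI, and the most extreme value of the illness is used. At a symptomatic visit the swab, respiratory rate and SpO2 are on the same form (Appendix D, Part 2a). Missed visits and hospital stays are filled in from medical records (Sections 9.2.1, 9.2.3 and 9.2.5), and a recognised deterioration must be captured with its worst values (Appendix D, Part 3). All of this stands, and it makes the path narrow. It does not close it: a deterioration that nobody observed leaves no values, and SpO2 in hospital is recorded only where available in air.

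A second reply is that deaths are watched closely. Fatal SAEs go to the iSRC and IDMC within 48 hours, holding rule 1a stops the trial for a death judged related, SAEs are described in detail, and Section 4 calls the case definitions complementary to standard safety tables. A reader might infer that deaths are lost to oversight; they are not. But none of these routes corrects the statistic in 11.11.

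A third reply is that the definitions are WHO-based and that handling of missing signs belongs in the SAP. The first part is a real cost of changing them. On the second, the protocol already fixes the classification through Table 6, so an SAP rule would have to depart from it.

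Two further readings are tempting and not supported.

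- One is that fatal cases defined the FI-RSV signal. Section 1.1.3.1 does report that "2 of the vaccinated children died, one at the age of 14 months, the other at the age of 16 months", but it defines FI-RSV enhanced disease by greater severity, and possibly duration, of RSV-LRTI symptoms, and the 80% in 11.4 is a hospitalization rate.
- The other is to size the problem by a fatality rate worked up from those two deaths. That would give the chance of any death, not of an unscored one, and both children were first vaccinated at 2 and 5 months, younger than this population.

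**Conclusion.** The point holds in limited form. Table 6 does not classify death as very severe RSV-LRTI, so a qRT-PCR-confirmed infant who dies with no qualifying SpO2 or respiratory rate on file is counted as a non-progression. It is a flaw in one statistical rule, not in safety oversight.

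How often it would occur cannot be derived from the documents. Under the assumed losses shown, the chance of wrongly excluding 80% stays below 5% at 6.25% and 12.5% and passes it at 25%. The case for acting rests on the small count: with about 5 infections, one such infant can turn a result that does not exclude 80% into one that does, or hold the count below the alarm rule. This assumes the planned 5 infections, exact limits, and the natural reading of Table 6 in which RSV-LRTI must be met first. It does not extend to infants without a positive nasal-swab qRT-PCR, who leave numerator and denominator together.

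**What to change.** Add to the very severe row of Table 6 and Synopsis Table 5: or death during an RSV-RTI or RSV-LRTI episode with RSV infection confirmed as in footnote 4, whether or not a qualifying SpO2 or respiratory rate was recorded. State in 11.10 and 11.11 that such a death counts as a progression. Naming both episode types also covers an infant who met RSV-LRTI but has none of the further signs on file.

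Keep one confirmation rule for numerator and denominator. Accepting any specimen for deaths alone would confirm them by a looser standard than other infections. Show RSV-positive deaths confirmed only by a local or other specimen in a sensitivity analysis that adds them to both.

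The cost is a line in the table, matching sentences in 11.10 and 11.11, and one extra table. Fatal SAEs are already collected, and the sample size, the cut-offs of 1 and 3 in 5, and the power of 91.9% are unchanged. Two small drawbacks should be stated: the definition departs from its WHO-based source, and an unrelated death during an RSV episode would count, which errs on the cautious side.

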## 5. STUDY COHORT

### 5.1. Number of subjects

The target will be to enroll approximately 150 infants likely to be previously unexposed to RSV with about 50 infants for each of three randomization groups. If necessary, the sample size *may* be increased through additional recruitment in order to achieve *a sufficient number of* RSV infected infants, with a negative RSV exposure status (at screening based on in-stream serological testing), in each RSV vaccine group. Dose 1 administration should be completed before the first RSV season and second dose will be given one month after the first dose (RSV seasons will be determined for each country based on local epidemiological data and documented in the SPM). The RSV season is defined as the period of the year when 70% of the RSV cases have occurred in previous years. For the calculation, where available, data from up to the ten previous years should be applied. If the data permit calculation of the actual date of the beginning of the season, rather than approximation to the nearest month, this is desirable. Refer to the SPM for RSV seasons per country. Refer to Section 11.4 for the determination of sample size **(Amended 1 August 2019)**.

*Overview of the screening plan:*

Upon completion of all screening procedures (refer to [Table 7](#)), the investigator will review the inclusion/exclusion criteria for each infant. Infants meeting all eligibility criteria will be enrolled in the study. Their screening information will be recorded on the appropriate screen of eCRF.

If the investigator believes there is a reasonable reason to do so, screening procedures may be repeated once only. All screening procedures may be repeated except the blood sampling for humoral response (neutralizing antibody titers against RSV-A, RSV-F protein antibody concentrations and palivizumab-competing antibody concentrations).

### 5.2. Inclusion criteria for enrolment

Deviations from inclusion criteria are not allowed because they can potentially jeopardize the scientific integrity, regulatory acceptability of the study or subject safety. Therefore, adherence to the criteria as specified in the protocol is essential.

All subjects must satisfy ALL the following criteria at study entry:

- Subjects' parent(s)/LAR(s) who, in the opinion of the investigator, can and will comply with the requirements of the protocol (e.g., completion of the diary cards, return for follow-up visits).
- Written informed consent obtained from the parent(s)/LAR(s) of the subject prior to performing any study specific procedure.
- A male or female between and including 6 and 7 months of age (from the day the infant becomes 6 months of age until the day before the infant achieves 8 months of age) at the time of the first vaccination.

- Healthy subjects as established by medical history and clinical examination before entering into the study.
- Born full-term (i.e., after a gestation period of 37 to less than 42 completed weeks) with a minimum birth weight of 2.5 kg.
- Subjects' parent(s)/LAR(s) need to have access to a consistent mean of telephone contact (e.g., land line or mobile) or computer.

### 5.3. Exclusion criteria for enrolment

Deviations from exclusion criteria are not allowed because they can potentially jeopardize the scientific integrity, regulatory acceptability of the study or subject safety. Therefore, adherence to the criteria as specified in the protocol is essential.

The following criteria should be checked at the time of study entry. If ANY exclusion criterion applies, the subject must not be included in the study:

- Child in care  
Please refer to the [glossary of terms](#) for the definition of child in care.
- Use of any investigational or non-registered product (drug or vaccine) other than the study vaccine during the period starting 30 days before the first dose of study vaccine (Day -29 to Day 1), or planned use during the study period.
- Chronic administration (defined as more than 14 days in total) of immunosuppressants or other immune-modifying drugs during the period starting six months prior to the first vaccine. For corticosteroids, this will mean prednisone  $\geq 0.5$  mg/kg/day (for pediatric subjects), or equivalent. Topical steroids are allowed.
- Administration of long-acting immune-modifying drugs (e.g., infliximab) or planned administration at any time during the study period.
- Administration of immunoglobulins and/or any blood products during the period starting three months before the first dose of study vaccine or planned administration during the study period.
- Planned administration/administration of a vaccine not foreseen by the study protocol in the period starting 30 days before the first dose and ending 30 days after the last dose of vaccine administration, with the exception of scheduled routine pediatric vaccines. (For details of permitted concomitant vaccines refer to Section 7.6). Scheduled routine pediatric vaccines may be administered  $\geq 7$  days before a dose of study vaccine or  $\geq 7$  days following a dose of study vaccine, with the exception of live viral vaccines which may be administered  $\geq 14$  days before a dose or  $\geq 7$  days after a dose.
- Acute or chronic, clinically significant pulmonary, cardiovascular, hepatic or renal functional abnormality, as determined by physical examination or laboratory screening tests.
- A history of, or on-going confirmed RSV disease or highly compatible clinical picture (e.g., bronchiolitis).

- Serious chronic illness.
- Major congenital defects.
- History of any neurological disorders or seizures.
- History of or current autoimmune disease.
- History of recurrent wheezing. (“Recurrent wheezing” is defined as  $\geq 2$  episodes of wheezing in the subject’s lifetime). Wheezing should have been verified on auscultation by doctor.
- History of chronic cough (4 weeks or more duration).
- Previous hospitalization for lower respiratory illnesses.
- Previous, current or planned administration of *Synagis* (palivizumab).
- Neurological complications following any prior vaccination.
- Born to a mother known or suspected to be HIV-positive (no laboratory testing required).
- Any confirmed or suspected immunosuppressive or immunodeficient condition, based on medical history and physical examination (no laboratory testing required).
- Family history of congenital or hereditary immunodeficiency.
- Previous vaccination with a recombinant simian or human adenoviral vaccine.
- History of any reaction or hypersensitivity to any component of the vaccines (investigational or control) or placebo used in this study or any contraindication to them.
- Hypersensitivity to latex.
- Current severe eczema.
- Acute disease and/or fever at the time of enrolment (Visit 1).
  - Fever is defined as temperature  $\geq 38.0^{\circ}\text{C} / 100.4^{\circ}\text{F}$ . The preferred location for measuring temperature in this study will be the rectum for subjects  $< 12$  months of age.
  - Clinically significant upper respiratory tract infection.
  - Subjects with a minor illness (such as mild diarrhea) without fever may be enrolled at the discretion of the investigator.
- Any clinically significant Grade 1 or any  $\geq$  Grade 2\* hematological or biochemical laboratory abnormality detected at the last screening blood sampling.

\* Refer to [APPENDIX C](#). For Grade 1 laboratory abnormalities, the investigator should use his/her clinical judgment to decide which ones are clinically relevant. Infants with hematological/biochemical values out of normal range which are expected to be temporary, may be re-screened at a later date.

- Any medical condition that in the judgment of the investigator would make IM injection unsafe.

- Any other conditions that the investigator judges may interfere with study procedures (e.g., drawing blood), findings (e.g., immune response).
- Any conditions that could constitute a risk for the subjects while participating to this study.
- Weight below the fifth percentile according to the World Health Organization (WHO) weight-for-age tables ([https://www.who.int/childgrowth/standards/weight\\_for\\_age/en/](https://www.who.int/childgrowth/standards/weight_for_age/en/)).
- Participating in another clinical study, at any time during the study period, in which the subject or mother (if breastfeeding) has been or will be exposed to an investigational or a non-investigational vaccine/product (pharmaceutical product or device)
- Planned move to a location that will prohibit participating in the trial until study end.
- For Thailand only, subjects who have received Synflorix prior to enrolment.

